Design & Setting: We will conduct a double-blind, randomised, parallel-group controlled superiority trial with alcohol treatment outpatients at 6 AOD treatment services in Melbourne, Victoria. Participants will be randomised to one of 2 groups with a 1:1 allocation ratio. Both participants and researchers completing the follow-up interviews will be unaware (blinded) of the condition to which they have been randomly allocated.

Participants: We aim to recruit at least 300 participants receiving outpatient interventions for alcohol use disorder at the participating services. To be eligible, participants must, at the time of the screening interview:

- Be aged 18+
- Own an Android or iOS smartphone with an Australian mobile number
- Be currently accessing outpatient treatment for alcohol problems. (There is no requirement that alcohol be the *only* substance for which they are seeking treatment, and as such participants with multiple drugs of concern are eligible as long as alcohol is one of the drugs of concern for the current episode of treatment.)
- Have an Alcohol Use Disorders Identification Test (AUDIT) score of at least 8
- Not have been in residential rehabilitation within the past 4 weeks.
- Not have been in any form of inpatient treatment (e.g. hospital or residential withdrawal treatment) within the past week.
- Not entering inpatient/residential treatment within the next month.

The target sample size was determined based on practical considerations (likely recruitment rate, time available for recruitment), as there was little prior basis to estimate likely effect size of a personalised ApBM smartphone app in an outpatient client population. Nevertheless, a calculation conducted in GPower 3.1 suggested that the primary analysis (across 4 repeated measures) would have 90% power to detect a small time x group interaction effect size (partial eta squared of .01) with a sample of 178 participants (i.e., 59% retention at follow-ups). If recruitment proceeds quickly enough, we will aim to recruit more than 300 participants, to allow for increased statistical power in case attrition is larger than expected.

Measures:

Demographic information: Participants will be asked to enter their gender, the AOD service where they were recruited from, the date they began the current episode of treatment they are receiving from that service, and drugs of concern, in an online survey hosted on Qualtrics.

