Audio-recorded qualitative interviews and verbal consent will be stored as .mp4 files on a secure Google drive hosted by Monash University, access to which will be restricted to project personnel (but which will not be made accessible to blinded quantitative data collectors until data collection is complete). The .mp4 files will be securely transferred to Pacific Transcription, a trusted transcription service provider that is frequently used by Monash University and Turning Point. To preserve participant anonymity the recording of verbal consent (where the participant states their full name and is also asked about their phone number) will be separated from the rest of the file and stored separately, while the main interview file will be labelled with a participant number (this number will be the same as the participant access code used to access the app, allowing baseline demographic data to be matched to qualitative interview data), not their name. Transcripts returned by Pacific Transcription will be stored as .docx files on the secure Google drive until data collection is complete. Once data collection is complete and blinding no longer required, these files will be stored in the project folder on the Turning Point Clinical Research Drive. They will be deleted from the Google Drive once analysis and publication is complete, and stored for at least 7 years following publication of the last paper arising from this study, or 7 years after the final report to the ethics committee, or 7 years after final reporting of outcomes on the clinical trials registry, whichever occurs latest.

Data Analysis

Statistical significance will be ascertained using $\alpha=.05$. Any participants who commenced at least 1 session of ApBM (if in the ApBM condition) or AAT (if in the minimal control condition) will be included in the analysis population.

Primary outcome: A linear mixed-effects model (LMM) will be used to compare change in mean standard drinks consumed per week between groups across 4 time points (baseline, post-intervention, 1-month follow-up, and 3-month follow-up). This model will test the main effects of time and group and (most crucially for determining efficacy) the group x time interaction. Planned follow-up comparisons between groups at post-intervention, 1-month follow-up, and 3-month

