follow-up time-points will be conducted using t-tests, with post-intervention being the primary endpoint. A secondary sensitivity analysis will be conducted excluding a participant's data from any time-point where they had been in residential/inpatient treatment in the past week (i.e., restricting analyses to time-points where a participant's opportunity to drink had not been limited by hospitalisation, rehabilitation, etc.). If a difference between groups is found post-intervention, a secondary LMM analysis of difference between groups in change in weekly standard drinks during the intervention period (i.e., 5 levels of time: Baseline, week 1, week 2, week 3, post-intervention) will be conducted to examine how quickly differences between groups emerge, with t-tests used to compare groups at week 1, 2, 3, and post-intervention time-points. This secondary analysis will be conducted excluding participants who had engaged in any residential/inpatient treatment within the intervention period.

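### The week-by-week analysis is meant to show how quickly group differences emerge, but nothing in it tests whether the group difference changes across weeks 1 to 4

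*Combined protocol and SAP*

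**What the plan says.** The analysis is described in the Data Analysis section, under Primary outcome.

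- **Condition:** "If a difference between groups is found post-intervention, a secondary LMM analysis of difference between groups in change in weekly standard drinks" over the intervention period is to be run.
- **Time levels:** "5 levels of time: Baseline, week 1, week 2, week 3, post-intervention".
- **Purpose and tests:** "to examine how quickly differences between groups emerge, with t-tests used to compare groups at week 1, 2, 3, and post-intervention time-points".
- **Population:** "This secondary analysis will be conducted excluding participants who had engaged in any residential/inpatient treatment within the intervention period".

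The same section gives the key test of the four-level primary model as "most crucially for determining efficacy) the group x time interaction". I take the week-by-week model to follow the same pattern, because no other test is named for it. The significance level is .05. Sidedness is not stated, and I assume two-sided t-tests.

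The plan specifies no contrast between weeks, no interaction restricted to weeks 1-4, no confidence interval for a change in the group difference, and no rule for reading onset from the weekly results.

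**The concern.** How quickly a difference emerges is a question about timing: is the effect already there at week 1, or does it build up to week 4? To tell these apart, the week-1 and week-4 group differences have to be compared. The planned tests each ask instead whether there is any difference.

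The natural ways to read their results are therefore unsafe. A significant five-level interaction fits immediate and gradual onset equally well. A pattern such as non-significant at weeks 1 and 2 but significant at weeks 3 and 4 can arise by chance from a constant effect, because one significant and one non-significant result do not show that the two differ. At stake is the published statement on speed of onset. The test of efficacy is not affected.

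**Working it through.** **1. The plan's own figure.** The Participants paragraph claims "90% power to detect a small time x group interaction effect size (partial eta squared of .01) with a sample of 178 participants" over four repeated measures. I assume a correlation of .5 and sphericity, neither of which is stated.

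- f² = .01/.99 = .0101
- λ = f²·N·m/(1−ρ) = .0101 × 178 × 4/.5 = 14.38, with df 3 and 528
- Power = .902, so 178 reproduces.

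**2. That effect in SD units.** Read partial eta squared .01 as a step: group difference 0 at baseline and d at the three later visits. Then f = d√3/8, so d = .1005/.2165 = 0.46. The documents give no SD or correlation for weekly drinks, so I use d = 0.2 to 0.46 and ρ = .5 to .7 as assumed ranges.

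**3. The null hypotheses.** Let Δ0 to Δ4 be the group differences at baseline and weeks 1-4. The design states "Participants will be randomised to one of 2 groups with a 1:1 allocation ratio", so randomisation makes the expected Δ0 zero.

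- Five-level interaction: Δ0 = Δ1 = Δ2 = Δ3 = Δ4, which then means no effect at any week.
- Each weekly t-test: Δw = 0.
- Timing question: Δ1 = Δ2 = Δ3 = Δ4, or Δ4 − Δ1 = 0. No planned test has this null.

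**4. Interaction under a constant effect from week 1.** With n per arm, unit SD and equal correlation, λ = (n/2)·Σ(Δ − mean Δ)²/(1−ρ). For the profile (0, d, d, d, d) the sum is 0.8d², so λ = 0.4nd²/(1−ρ). Rejection rates from the noncentral F (df 4 and 2n−5), for ρ = .5 to .7:

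| N | d | λ | Five-level interaction rejects |
|---|---|---|---|
| 178 | 0.2 | 2.85-4.75 | 23-37% |
| 178 | 0.3 | 6.41-10.68 | 49-74% |
| 178 | 0.46 | 15.34-25.57 | 89-99% |
| 300 | 0.2 | 4.80-8.00 | 38-60% |
| 300 | 0.3 | 10.80-18.00 | 75-94% |
| 300 | 0.46 | 25.86-43.10 | 99% or more |

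Simulation gives about 25-100% over the same grid. Over weeks 1-4 only, the sum is 0, so λ = 0 and the test rejects at 5%. Simulated rates are about 4-6% for the weeks 1-4 interaction and for the week-4-minus-week-1 contrast.

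**5. Weekly t-tests under the same constant effect.** I take the condition for running the model as a significant post-intervention t-test. Simulated probability, given that condition, that week 1 is non-significant:

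| N | d = 0.2 | d = 0.3 | d = 0.46 |
|---|---|---|---|
| 178 | 41-51% | 24-32% | 7-11% |
| 300 | 30-39% | 14-18% | under 2% |

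**6. Power of a timing test for a gradual effect** (0.1, 0.2, 0.3, 0.4 SD at weeks 1-4).

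- Weeks 1-4 interaction: the squared deviations from the mean of 0.25 sum to .05, so λ = (n/2)(.05)/(1−ρ). This is 4.45-7.42 at N=178 and 7.50-12.50 at N=300. Simulated power is about 37-62% and 62-84%.
- Week-4-minus-week-1 contrast: 0.3/√(4(1−ρ)/n) = 2.00-2.58 at N=178 and 2.60-3.35 at N=300. Simulated power is about 51-74% and 73-92%.

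**The case against.** The strongest reply is that the plan never commits the misreading. It does not say that a significant interaction means gradual onset, that a non-significant week means the effect has not yet emerged, or that the first p<.05 defines onset. In the primary model the interaction's role is efficacy. On that view the rates in step 4 are the power of an efficacy test, and rejecting is correct because a difference did emerge between baseline and week 1. This stands: those figures show that the interaction does not discriminate between onset patterns. They are not a false-positive rate of the plan.

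A reader might also infer that the analysis cannot say anything about timing. That is too strong. Emergence can be measured from baseline, and the five-level model yields all four weekly differences and already contains the contrast that is needed.

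Nor should the risk be overstated. The three events together (condition met, interaction significant, week 1 non-significant) occur in about 4-10% of trials at N=178 and 2-10% at N=300. The high week-1 miss rates belong to small effects, where the condition is itself met less often: in about 26% of trials at d = 0.2 and N=178.

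Finally, a reader might infer consequences for how many sessions are thought necessary. No section uses this analysis for that purpose, and none of the nine hypotheses concerns timing.

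What remains is that a timing question is posed, no test of it is specified, and no rule guards against reading onset from the weekly p-values.

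**Conclusion.** The point holds as a minor improvement to a secondary, conditional analysis. The planned interaction cannot separate immediate from gradual onset. The pattern of weekly p-values can mislead about onset, materially if the true effect is 0.2-0.3 SD, modestly at the effect the trial was sized for with N=178, and hardly at all at that effect with N=300.

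A reader might infer that the efficacy result is compromised. The documents do not support that: efficacy rests on the four-level primary model and its post-intervention comparison, which this analysis only follows.

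The figures assume normal, complete data, equal correlations between weeks, and chosen values of d and ρ. Skewed drinking counts, missing weekly reports and the exclusion of participants with residential or inpatient treatment were not modelled.

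**What to change.** Keep the five-level model. In the Primary outcome paragraph of the Data Analysis section, add:

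- one pre-specified between-week test of the group difference with its 95% CI: either week 4 minus week 1 from the fitted model, or group x week over weeks 1-4 with baseline weekly drinks as a covariate;
- the four weekly group differences, each with a 95% CI;
- a statement that onset will not be inferred from the first week with p<.05, and that a non-significant between-week test will not be read as proof of immediate onset.

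This costs a sentence or two of wording and no new data. The drawback is the limited power for gradual onset shown in step 6, so the conclusion on timing may stay open. The single contrast is the more powerful of the two options for the steady build-up examined there. The last statement is needed because, with this power, a null result would otherwise invite the opposite error.

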1. Participants randomised to ApBM will consume significantly fewer standard drinks per week than participants in the minimal condition, as measured using self-report 4 weeks after commencing training (post-intervention; primary endpoint), and at 1-month and 3-month follow-ups (secondary endpoints).

Secondary outcomes:

2. Participants randomised to ApBM will show significantly larger declines, compared to those in the minimal condition, in past-week frequency of alcohol craving at post-intervention and follow-up assessments (relative to baseline craving frequency), as assessed by the frequency scale of the Craving Experience Questionnaire.
3. Participants randomised to ApBM will show significantly larger declines than those in the minimal condition in Severity of Dependence Scale scores at post-intervention and follow-up assessments (relative to baseline craving frequency).
4. Participants randomised to ApBM will show significantly larger declines than those in the minimal condition in Alcohol Use Disorders Identification Test (AUDIT) scores at the 3-month follow-up (relative to baseline scores).
5. Participants randomised to ApBM will have significantly fewer past-week heavy drinking days (HDDs, defined as ≥ 5 standard drinks in a day) than participants in the minimal

condition, as measured using self-report at post-intervention, 1-month, and 3-month follow-ups. Past-month HDDs will also be analysed post-intervention.

6. Participants randomised to ApBM will have significantly fewer past-month drinking days (i.e., days on which any alcohol is consumed) post-intervention and at 1- and 3-month follow-ups.
7. The proportion of participants reporting complete abstinence (i.e., 0 days on which any alcohol was consumed – both past week and past month will be analysed) will be significantly higher among participants in the ApBM than among those in the minimal condition at post-intervention and follow-up assessments.
8. Participants receiving ApBM will experience larger increases than those in the minimal condition in quality of life and health (assessed with 3 Australian Treatment Outcome Profile items) at post-intervention and follow-up assessments (relative to baseline).
9. There will be a significantly greater reduction in approach bias, as measured by the alcohol approach avoidance task, in participants assigned to the ApBM condition, compared to those in the minimal condition, between baseline and post-intervention.

Methods

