Secondary outcomes: Continuous outcome variables (CEQ, SDS, AUDIT, past-week HDDs, past-month drinking days, ATOP items, and approach bias) will be analysed in a similar manner to the primary analysis described above. In analyses of CEQ, SDS, past-week HDDs, past-month drinking days, and the 3 ATOP items, there will be 4 levels of time (baseline, post-intervention, 1-month, and 3-month follow-ups). Sensitivity analysis of past-week drinking days to control for the possible effect of past-week residential/inpatient treatment will be conducted as described for the primary outcome. Past-month drinking days will be expressed as a percentage of the total number of days on which a participant had the opportunity to drink (i.e., if a participant was in residential/inpatient treatment for 10 days at a certain time point, then for that time point, their past-month drinking days will be expressed as a proportion of the remaining 18 days on which they had the opportunity to drink), although data will be excluded at any time point where the participant did not have at least 14 days on which they had the opportunity to drink alcohol (i.e., if they were within residential/inpatient treatment on 15 or more days). For CEQ, secondary analyses will be conducted for each of its 3 subscales. Analyses of AUDIT scores will use 2 levels of time (baseline, 3-month follow-up). Approach bias analyses will also use 2 levels of time (baseline, post-intervention) and approach bias scores will be analysed separately for alcohol and positive images. As past-month HDDs can only be calculated at 1 time point (post-intervention), they will simply be compared between groups using a t-test post-intervention after converting scores to a proportion of days on which the participant had an opportunity to drink (as described for past-month drinking days). Proportions of groups reporting complete past-week and past-month abstinence will be compared between groups at post-intervention, 1-month follow-up, and 3-month follow-up using Pearson's chi-squared. uMARS "functionality", "aesthetics", and "subjective quality" scores, and participants' subjective ratings regarding AAT-App's effect on drinking and cravings will be explored within each group separately using descriptive data (e.g., mean, median, quartile cut-offs, percentages scoring above 3) to quantify typical ratings and proportions of participants providing favourable ratings. Where relevant, exploratory analyses will also compare mean scores of uMARS scales between groups using t-tests.

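### Abstinence has no opportunity-to-drink rule, so a long residential stay removes a participant from past-month drinking days but counts as a past-month abstinence success

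*Combined protocol and SAP*

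**What the plan says.** All references are to the combined protocol and SAP.

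- **Primary outcome** (Data Analysis, Primary outcome): weekly standard drinks get a sensitivity analysis that drops any time point with residential or inpatient treatment in the past week.
- **Past-month drinking days** (Data Analysis, Secondary outcomes): expressed as a percentage of the days on which the participant could drink, and "data will be excluded at any time point where the participant did not have at least 14 days" of opportunity.
- **Past-month HDDs** (same section): converted to a proportion of opportunity days by reference to the drinking-days method.
- **Abstinence** (Aims and Hypotheses, hypothesis 7): defined as "0 days on which any alcohol was consumed – both past week and past month will be analysed". The analysis reads "Proportions of groups reporting complete past-week and past-month abstinence will be compared between groups" at three time points by Pearson's chi-squared. No denominator, exclusion or sensitivity analysis is attached.
- **Past-week check for secondary outcomes** (Data Analysis, Secondary outcomes): "Sensitivity analysis of past-week drinking days to control for the possible effect of past-week residential/inpatient treatment" is to follow the primary-outcome method. That variable appears neither in the hypotheses nor in the section's list of continuous outcomes, which has past-week HDDs and past-month drinking days. Under Measures, Alcohol consumption, it is only a derived quantity.

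**The concern.** The plan recognises that days in residential care distort drinking measures and deals with this for the other past-month calendar outcomes, but not for abstinence. Yet abstinence is the outcome that a full stay in care can settle outright: someone with no chance to drink meets the definition automatically.

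Two things are at stake. First, the trial report would handle one participant at one time point in two opposite ways, using the same calendar. Second, the between-group abstinence comparison would partly measure how many people in each arm were in residential care. If that share is equal, a real difference shrinks. If it is unequal, the difference shifts towards the arm with more residential use, whichever that is.

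The misnamed variable is a smaller, separate matter. As written, the past-week sensitivity analysis is attached to something that the plan does not otherwise compare between groups.

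**Working it through.** **1. The plan's own arithmetic.** It is consistent. Its example is 28 − 10 = 18 opportunity days. At 15 residential days, 28 − 15 = 13, which is below 14, so the time point is excluded. At 14 residential days, 28 − 14 = 14, so it is kept.

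**2. The rules side by side.**

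| Outcome | Opportunity rule or check |
|---|---|
| Weekly standard drinks (primary) | Sensitivity analysis, past-week residential treatment |
| Past-month drinking days | Opportunity-day denominator; excluded below 14 days |
| Past-month HDDs | Same conversion |
| Past-week HDDs | Unclear: see the objection below |
| Past-week abstinence | None |
| Past-month abstinence | None |

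**3. Two participants followed through.**
- 28 residential days, no drinking: 28 − 28 = 0 opportunity days, so excluded from past-month drinking days; counted as past-month abstinent.
- 7 residential days in the past week, no drinking in that week: dropped from the primary outcome's sensitivity analysis; counted as past-week abstinent with no corresponding check.

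**4. Can it happen?** Yes. Eligibility (Methods, Participants) bars only those entering inpatient or residential treatment within the next month, and the Procedure section places no limit on other care during the intervention or follow-up. The 28-day recall at the 1-month follow-up (day 56) starts at about day 56 − 28 = 28, so it lies largely beyond that screen.

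**5. Effect on the difference.** Let p be the abstinence rate among participants not in residential care and r the share in residential care, all of whom are counted as abstinent. The counted rate is p(1 − r) + r. The documents give neither p nor r. Assume p = 25% (active) and 15% (control), a true difference of 10 points:

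| r active / control | Counted active | Counted control | Difference |
|---|---|---|---|
| 4% / 8% | 0.96 × 0.25 + 0.04 = 28.0% | 0.92 × 0.15 + 0.08 = 21.8% | 6.2 points |
| 6% / 6% | 0.94 × 0.25 + 0.06 = 29.5% | 0.94 × 0.15 + 0.06 = 20.1% | 9.4 points |
| 8% / 4% | 0.92 × 0.25 + 0.08 = 31.0% | 0.96 × 0.15 + 0.04 = 18.4% | 12.6 points |

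**6. Effect on the test.** For scale, take the plan's retained sample. Its claim of "90% power to detect a small time x group interaction effect size (partial eta squared of .01) with a sample of 178 participants" reproduces if a correlation of 0.5 and sphericity are assumed (the plan states neither): f² = 0.01/0.99, λ = 178 × 4 × f²/0.5 = 14.4, degrees of freedom 3 and 528, power 0.902. Retention is 178/300 = 59.3%. With 1:1 allocation, n = 178/2 = 89 per arm. Power for two proportions p₁ and p₂ with difference d and mean p̄ is Φ{[|d| − 1.96√(2p̄(1 − p̄)/n)] / √[(p₁(1 − p₁) + p₂(1 − p₂))/n]}.

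*Equal residential use, assumed true abstinence 40% vs 20%* (counted difference = 20 × (1 − r); on exclusion, n becomes 89(1 − r) and the difference stays at 20 points):

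| r in both arms | Counted difference | Power, all counted | Power, residential excluded |
|---|---|---|---|
| 0% | 20 points | 0.835 | 0.835 |
| 5% | 19 points | 0.771 | 0.816 |
| 10% | 18 points | 0.704 | 0.794 |
| 20% | 16 points | 0.576 | 0.745 |

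*No true effect, unequal use.* The false difference is (1 − p) × (difference in r). For p from 35% down to 15%:
- r of 5% vs 10%: 3.25 to 4.25 points; the test rejects in favour of the arm with more residential use in about 7% to 10% of trials.
- r of 5% vs 15%: 6.5 to 8.5 points; about 14% to 27% of trials.

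The nominal rate in that one direction is 2.5%. With equal use there is no false difference.

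**The case against.** **Counting all observed abstinence is a legitimate choice.** Hypothesis 7 asks only whether any alcohol was consumed, and other care is unrestricted, so abstinence achieved with the help of an admission can fairly count. This stands, and it is why the all-participant analysis should stay. It does not explain why other outcomes from the same calendar are treated differently without comment.

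**Past-week HDDs are probably covered.** A reader might infer that past-week HDDs are as unprotected as abstinence. The text does not support this. The plan says that continuous outcomes, naming past-week HDDs, are analysed along the lines of the primary outcome, whose description includes the residential sensitivity analysis. The odd variable name is most likely a slip for past-week HDDs. That wording cannot reach abstinence, which is binary and has its own test.

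**Direction and cause are unknown.** A reader might take an admission as a sign of relapse and conclude that abstinence successes are falsely credited to one particular arm. The documents count any hospitalisation, withdrawal treatment or rehabilitation and give no reasons or rates, so neither the cause nor the direction follows.

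**The problem may be rare, and the illustration is an upper case.** The eligibility screen should make stays less common at post-intervention. Counting every residential participant as abstinent also overstates the past-month effect, since abstinence requires no drinking on the days outside care as well. Both points stand and limit the size.

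**Exclusion has its own bias.** Admission occurs after randomisation, so dropping these participants can distort the comparison. This stands and rules out making exclusion the main analysis.

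**Conclusion.** The point holds as an internal inconsistency: past-week and past-month abstinence lack any opportunity rule or check, and at 15 or more residential days without drinking the plan treats the same participant in opposite ways for past-month drinking days and past-month abstinence. The sensitivity sentence also needs correcting, as a matter of wording.

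The size cannot be stated from the documents. The range of 6.2 to 12.6 points around a true 10 rests on assumed abstinence and residential rates, and on counting everyone in care as abstinent. A reader might take the lowest value as showing that the plan loses 38% of the effect (3.8/10). It does not: that figure depends on assuming more residential use in the control arm, and reversing the imbalance increases the difference instead.

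The primary analysis and sample size are unaffected. This is a cheap improvement for secondary outcomes only.

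**What to change.** In Data Analysis, Secondary outcomes:

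1. Keep the chi-squared comparison of abstinence in all participants.
2. For past-week abstinence, add a sensitivity analysis excluding time points with any past-week residential or inpatient treatment, as for the primary outcome.
3. For past-month abstinence, add a sensitivity analysis excluding time points with fewer than 14 opportunity days, as for past-month drinking days.
4. Report both versions together, with residential use by arm at each time point.
5. Correct the past-week sensitivity sentence to name the intended listed outcome: past-week HDDs, if that was meant.

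Cost: a few sentences and extra runs, best settled before unblinded analysis. Residential days are already asked about at every assessment after baseline. The Procedure section spells out the past-week question only for the post-test survey, so confirm that it is also in the two follow-up surveys; the primary outcome's sensitivity analysis needs it anyway.

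Downsides: a slightly smaller N in the added runs, and possible bias from excluding on a post-randomisation event, which is why these remain sensitivity analyses. The 14-day rule is also a partial remedy: someone with exactly 14 residential days and no drinking still counts as abstinent.
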